7.1 Screening

All patients who underwent primary total knee arthroplasty from January 2011 to December 2015 at the Orthopaedics Unit of the C.O.Q. Hospital in Omegna will be identified through hospital database. If deemed eligible according to the inclusion/exclusion criteria, patients will be contacted by telephone by the principal investigator or one of his representatives and invited to take part in the study. If possible, the patient information sheet, the patient's informed consent form and the information on the processing of personal data will be sent by ordinary post or e-mail. The investigator will invite each patient eligible for the study to present themselves at the C.O.Q. Orthopaedics Unit for a follow-up and will be invited to present themselves with all the radiographic documentation in their possession.

7.2 Enrolment

The principal investigator, or one of his representatives, will explain to the patient the reasons and methods for carrying out the study and provide all the necessary information before enrolment. The patient will be given the Patient Informed Consent form, the Consent to the Processing of Personal Data form. Furthermore, the investigator will be available to provide an adequate response to any questions or concerns expressed by the patient. The investigator will advise the patient to carefully and calmly read the Patient Informed Consent and Consent to the Processing of Personal Data forms and to discuss their contents with their family, friends and doctor before making any decision

in this regard. The patient will give his informed consent by completing and signing the printed Patient Informed Consent and Consent to the Processing of Personal Data forms. From this point on the patient will be considered enrolled in the study.

7.3 Follow-up visit

At the follow-up visit, an objective evaluation of the operated knee will be carried out, questions will be asked about the patient's current state of health, as well as a radiographic follow-up evaluation will be carried out assessing the last anterior-posterior and lateral knee radiographs compared with the first postoperative radiograph.

If the patient has signed the Informed Consent and the Consent to the Processing of Personal Data, the information requested in the case report forms described below will be recorded.

7.4 End of the study

To complete the individual patient study, the recording of all information required in all case report forms must be complete. These forms must also be completed in the event of spontaneous withdrawal from the study, loss of follow-up, failure and surgical revision of the implant. If some information is not available, the blank fields must be crossed out. The study is considered completed once all case report forms have been completed for all patients deemed eligible for the study.

8. Data recording and management

8.1 Case Report Forms (CRF)

For data recording according to this protocol, specific data collection forms, or case report forms (CRF), are prepared. The information reported in anonymous fashion on the CRFs must be recorded for each patient included in the study. Patients will be identified through their name/surname initials following a progressive number. Only the principal investigator will know the 1:1 association between patient and his ID. The CRFs, annexed to this protocol, are the following:

1. Medical history. General data of the patient, age, weight, height, diagnosis, medical history, previous medical history, known allergies, osteoporosis.
2. Intervention. Prosthetic implant information, the operation date, tibial insert material, whether conventional polyethylene without vitamin E or vitamin E polyethylene (respectively, control group or treatment group), are recorded.
3. AKSS. Knee-specific clinical evaluation score that the investigator completes at the last follow-up during the patient's follow-up visit [19].
4. FJS-12. Clinical evaluation score on the patient's awareness on his prosthesis, to be filled by the patient himself at the last follow-up [20].
5. Radiographic evaluation. Form that the investigators complete by evaluating and comparing the first postoperative radiograph taken after surgery and the anterior-posterior and lateral knee radiographs taken at the last follow-up. The radiographic signs showing the presence of any periprosthetic radiolucency lines or areas of periprosthetic osteolysis, signs of prosthetic loosening and component position will be recorded for each periprosthetic zone according to the "Modern Knee Society Radiographic Evaluation System and Methodology for Total Knee Arthroplasty".

6. Complications. Form to be completed in case of presence of one or more intraoperative or postoperative complications recorded through assessment of the patient's medical records, or at the first telephone contact or during the follow-up visit.
7. Implant outcome. Form to be completed to establish whether the patient has been contacted and/or visited, lost to follow-up, or deceased. Furthermore, the outcome of the prosthetic implant, i.e. whether it is still in place and well functioning, whether and when it was failed and surgically removed (revised) or whether it was failed with reoperation but not surgical removed, is recorded. By completing this form, it will be possible to complete the study flowchart like the following shown in Figure 3 to describe the outcome of the entire study population.

[figure not shown]

Figure 3. Descriptive flowchart of the study population.

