Furthermore, nothing has yet been published in the literature on mid-term results in primary total knee arthroplasty with polyethylene insert added with vitamin E. The maximum follow-up reported from clinical studies in total knee arthroplasty is in fact 3 years.

A study that reports the medium-term results of a series of total knee arthroplasties using polyethylene with vitamin E and comparing them with those of an identical insert but made of conventional polyethylene is therefore considered scientifically valid and well-founded.

The present study therefore aims to verify the survival, clinical and radiographic results of a consecutive series of patients undergoing first-time total knee arthroplasty with a polyethylene insert added with vitamin E, comparing them with an identical insert but made of polyethylene standard, at a minimum follow-up of 7 years.

3. Study design

Observational, cross-sectional, comparative, monocentric clinical study with a retrospective cohort. The study is promoted and sponsored by Permedica S.p.A., [name], Italy <https://www.permedica.it/>. The study centre is the Quadrante Orthopaedics Center (C.O.Q.) Hospital, placed in [name] - Italy. Study principal investigator (PI) will be [name]. The study will be conducted by PI and other co-investigators, PI's collaborators of the Orthopaedics Unit at C.O.Q. Hospital in Omegna and external collaborators of the CTO Hospital of Turin, coordinated by [name], Director of the Orthopaedics Unit and Traumatology 1, CTO Hospital of Turin. The study, being observational, will only concern

the collection of data about the patient, his medical history and pathology, his surgery and prosthetic implant and the clinical and radiographic results. The patient will be contacted by telephone and invited to a follow-up visit. Clinical scores will be recorded by the patient and the investigators, radiographic signs will be recorded from preoperative and postoperative radiographs performed at the last follow-up. The study will therefore not require any additional diagnostic or therapeutic services compared to the standard clinical practice. The study will only take into consideration patients who have already undergone total knee arthroplasty at the C.O.Q. Orthopaedics Unit.

4. Study objective

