8.3 Data entry, analysis and storage

All printed CRFs number 1-7, fully completed and signed in original, must be grouped together in one folder per patient. The original completed CRFs will be stored by the principal investigator in a specific study file, for a period of 15 years at the study centre. A copy of the completed CRFs will be stored by the sponsor in a specific study file, for a period of 15 years at the sponsor facility. Principal investigator and sponsor have the responsibility for data management. The CRF data will be entered by the sponsor into a single electronic database protected by password, which will undergo periodic back-up after each new data entry. The sponsor will have the responsibility for data analysis. At the end of the study, a PDF/A copy of the database file will be stored at the sponsor server and, moreover, will be saved on CD and other external memory and stored at the sponsor facility.

9. Duration of the study

The study will begin following the Ethics Committee approval and after the authorization from the C.O.Q. Management to start the study. A duration of approximately 12 months is estimated for patient screening, telephone contact, follow-up visits and data recording. The study will end with the completion of all the forms required for all enrolled patients. The duration of data entry from the paper CRF format to the electronic database is approximately 1 week but can be carried out at the same time as data collection. An additional 2 months are estimated for data analysis and drafting of the study report.

10. Statistical analysis

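### The protocol does not require those who score the AKSS or read the radiographs to be unaware of the insert type, so these secondary comparisons are open to assessor bias.

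*Combined protocol and SAP*

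**What the plan says.** Section 4.2 lists the American Knee Society Score (Knee and Function) and the radiographic signs (radiolucent lines and osteolysis) as secondary endpoints.

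Section 3 says of the scores: "Clinical scores will be recorded by the patient and the investigators". Section 8.1 gives the detail by form:

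- CRF 2 (Intervention): "tibial insert material, whether conventional polyethylene without vitamin E or vitamin E polyethylene (respectively, control group or treatment group), are recorded". The form therefore carries the group label. The sentence does not say who fills it in.
- CRF 3 (AKSS): "Knee-specific clinical evaluation score that the investigator completes at the last follow-up during the patient's follow-up visit".
- CRF 5 (Radiographic evaluation): "Form that the investigators complete by evaluating and comparing the first postoperative radiograph taken after surgery" with the last anterior-posterior and lateral films. Signs are recorded by periprosthetic zone under a named system.

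Section 8.3 says that completed and signed CRFs 1 to 7 "must be grouped together in one folder per patient". Section 3 describes the investigators as staff of the treating unit together with "external collaborators of the CTO Hospital of Turin".

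The supplied text does not mention masking, independent or coded film reading, or an order in which the forms are completed. The patient code in Section 8.1 protects identity only; it does not hide the insert. The annexed CRF templates were not available, so this statement covers the text of the protocol alone.

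**The concern.** The AKSS is scored by an examiner, and the reading of radiolucent lines depends on judgement. If the assessor knows which insert is in the knee, expectation can move the result in one direction. This is a sponsored comparison of two of the sponsor's own inserts.

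Such a shift is bias, not noise. More knees narrow the confidence interval around the wrong value. The planned analysis in Section 10.2 (t test or Mann-Whitney for continuous variables, Chi-square or Fisher for dichotomous ones) would neither detect nor correct it.

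At stake is whether a reported difference, or absence of difference, in AKSS or radiographic signs can be attributed to the insert. The FJS-12 is completed by the patient and lies outside this point.

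**Working it through.** **1. The plan's own figure.** The only related number is the sample size in Section 10.1. Inputs: survival 97.2% (control) and 97.7% (vitamin E), margin 4%, alpha 5%, power 80%.

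n = (0.972 × 0.028 + 0.977 × 0.023) × (1.645 + 0.842)² / (0.04 + 0.005)² = 151.7, rounded up to 152 per group.

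This reproduces with alpha taken as one-sided. Assessor masking does not enter the formula, so 152 stands.

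**2. What the text establishes.**

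| Question | Source | Answer |
|---|---|---|
| Are AKSS and radiographic signs endpoints? | 4.2 | Yes, secondary |
| Who scores them? | 3; 8.1 items 3 and 5 | Investigators |
| Is the insert type on a study form? | 8.1 item 2 | Yes, CRF 2 |
| Is it kept from the assessors? | Whole supplied text | No provision |
| Do the assessors in fact know it? | Whole supplied text | Not stated |

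The gap is the fourth row. The fifth row limits what can be claimed.

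**3. Illustration for the AKSS.** The documents give no standard deviation and no size of assessor lean; both are assumed here, for either AKSS component. There is no true difference, 152 knees per group, normal approximation, two-sided 5%.

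SE = SD × √(2/152). For SD 15 this is 1.72 points.

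Rejection probability = Φ(shift/SE − 1.96) + Φ(−shift/SE − 1.96).

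| Assumed SD | Lean of 2 points | Lean of 3 points |
|---|---|---|
| 12 | 30.6% | 58.7% |
| 15 | 21.3% | 41.4% |
| 20 | 14.1% | 25.8% |

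**4. Illustration for radiolucent lines.** Assume a true prevalence of 10% in both groups, with 20% or 30% of the lines passed over in one group. The observed rates become 10% against 8% or 7%, a false gap of 2 or 3 percentage points.

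- 2 points: SE = √[(0.10 × 0.90 + 0.08 × 0.92)/152] = 0.0328; shift/SE = 0.61; rejection about 9%.
- 3 points: SE = √[(0.10 × 0.90 + 0.07 × 0.93)/152] = 0.0319; shift/SE = 0.94; rejection about 16%.

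A larger distortion is needed for a large effect. Over-reading one group by 5 points from a 10% base gives about 26%, and from bases of 5% to 20% about 38% to 18%.

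**The case against.** The strongest reply is that the protocol is silent on what assessors know, and silence is not evidence that they know the insert. Much of that stands, and it rules out several stronger readings that a reader might infer.

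- *That the assessors know the insert type.* This is plausible: patients are found through the hospital database, each group must reach its own count, and investigators include staff of the treating unit. But no section says it, or that one person completes CRFs 2, 3 and 5.
- *That the shared folder puts the label in the assessor's hand.* Section 8.3 concerns the filing of forms already completed and signed. It does not describe what is on the table at the visit.
- *That film reading feeds into how failures are classified.* The primary failure is a revision for aseptic loosening, and CRF 7 records whether and when the implant was removed. Nothing in the text makes CRF 5 an input to the cause of revision.
- *That full masking is available with existing staff.* For films it is feasible. For the AKSS, scored in person at the treating unit, no section shows that an unaware examiner exists, and reordering forms does not help if the examiner already knows the case.

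Two practical objections also stand. The study ID contains initials, so it is not a neutral film label. Section 11.5 bars disclosure of personal data outside the study centre, which constrains reading films in Turin.

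Zone-by-zone recording under a named system limits discretion somewhat, but it does not replace masking. None of this supplies the missing safeguard.

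**Conclusion.** The concern holds in a limited form. The supplied protocol does not require AKSS examiners or film readers to be unaware of the insert, so both secondary comparisons are exposed to assessor bias. The conclusion goes no further than that: bias is possible and unguarded against, not shown to occur.

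Its size cannot be derived from the documents. On the assumed values, the AKSS false-positive rate would lie between about 14% and 59% for a lean of 2 to 3 points, and the radiographic rate would be about 9% to 16% for a false gap of 2 to 3 percentage points. The radiographic effect is modest unless the misreading is larger. The primary endpoint and sample size are untouched. The change is worth making because it is cheap.

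**What to change.** In Sections 7.3 and 8.1:

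1. Have the first postoperative and last films read under a neutral code, without initials or insert type, by an investigator already on the study who has no access to CRF 2 or the operation record. The external co-investigators are an obvious choice. Reading can take place at the study centre, or on de-identified copies handled consistently with Section 11.5. Section 5 gives both inserts the same design; that the films do not reveal the group is an assumption to confirm.
2. Require CRF 3 and CRF 5 to be signed before CRF 2 is available to the assessor.
3. State in the report that the AKSS was not fully masked wherever the examiner may know the insert.

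The cost is a small burden of coding and handling films and of controlling the order of forms. No visit, test or change in care is added. Masking of the AKSS remains partial, since an examiner from the treating unit may recall a case.

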4.2 Secondary endpoints

The secondary objectives of the study are survival for any reason, clinical results and radiographic results, prevalence of complications. Secondary endpoints are therefore:

- Survival of the prosthetic implant with vitamin E polyethylene and with conventional polyethylene, with revision for any reason as the end-point,
- the American Knee Society Score (KSS) with Knee score and Function score,
- the Forgotten Joint Score (FKS-12),
- Number of reinterventions (without any component removal), non-surgical complications and adverse events,
- Periprosthetic radiolucent lines and radiographic signs of periprosthetic osteolysis.

5. Prosthetic device

The medical device under investigation is a cemented bicompartimental knee prosthesis with a rotating tibial plateau, the GKS Prime Flex Mobile Bioloy® by Permedica S.p.A. (Figure 1). The femoral and tibial components are both coated with a titanium-niobium nitride (TiNbN) ceramic coating with 4.5 ± 1.5 microns thickness (Bioloy®). The femoral and tibial component are both cemented. The rotating tibial insert has an ultra-congruent articular surface and is made with

UHMWPE blended with vitamin E (0.1% alpha-Tocopherol), non-cross-linked and sterilized by ethylene oxide (VitaE®), or with conventional non-cross-linked UHMWPE (Figure 2).

Figure 1. Cemented mobile-bearing total knee prosthesis with TiNbN coating, GKS Prime Flex Mobile Bioloy® by Permedica S.p.A.

[figure not shown]

Figure 2. A: UHMWPE blended with 0.1% vitamin E, non-cross-linked and ethylene oxide sterilized (VitaE®) ultra-congruent rotating insert. B: Conventional, non-cross-linked, E-beam sterilized UHMWPE ultra-congruent rotating insert with same design.

6. Study population

The study will concern a consecutive series of patients who underwent primary total knee arthroplasty with the same knee prosthesis at the C.O.Q. hospital in Omegna (VB), Italy, from January 2011 to December 2015 and who will meet all eligibility criteria.

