10.2 Outcome analysis

Cumulative survival is calculated according to the Kaplan-Meier method [21], indicating the 95% confidence interval. Descriptive analysis to summarize the data and study results will be carried out by calculating mean, standard deviation and range of minimum and maximum values for continuous variables and by number and percentage for dichotomous variables. Data distribution was tested for normality with Shapiro-Wilk and D'Agostino Pearson tests.

The analysis of survival rates with 95% confidence intervals of study group versus control group will be performed with logarithmic rank test placing statistical significance at a p-value < 0.05.

The analysis of the differences between the 2 groups regarding the continuous variables will be carried out with Student's t test, while Mann-Whitney U test was used when distribution resulted not normal. The analysis of differences in dichotomous variables will be carried out with Chi-Square or Fisher's Exact tests if at least one of the variables has a value ≤ 5 .

The analysis will be carried out with one of the most used statistical software for this type of analysis (GraphPad Prism 10.1.0 Software, Boston, MA, USA).

11. Ethical and regulatory considerations

This clinical investigation is conducted in compliance with the ethical principles set out in the Declaration of Helsinki [22].

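### Reinterventions and postoperative complications are compared as crude percentages, with no stated denominator and no allowance for unequal observation time

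*Combined protocol and SAP*

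**What the plan says.** Section 4.2 lists as a secondary endpoint the "Number of reinterventions (without any component removal), non-surgical complications and adverse events", and words the matching objective as "clinical results and radiographic results, prevalence of complications". Neither states a time frame or a denominator.

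Section 10.2 summarises binary outcomes "by number and percentage for dichotomous variables". For the comparison it says: "The analysis of differences in dichotomous variables will be carried out with Chi-Square or Fisher's Exact tests". The only method there that uses follow-up time is for implant survival: "Cumulative survival is calculated according to the Kaplan-Meier method [21], indicating the 95% confidence interval", with a log-rank comparison.

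Section 8.1 describes how the events are collected:

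- CRF 6 (Complications) is a "Form to be completed in case of presence of one or more intraoperative or postoperative complications", with events "recorded through assessment of the patient's medical records, or at the first telephone contact or during the follow-up visit".
- CRF 7 (Implant outcome) serves "to establish whether the patient has been contacted and/or visited, lost to follow-up, or deceased". It also records revision and when it happened, and reoperation without removal of the implant. As summarised, timing is attached to revision but not to reoperation.

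Other sections bear on who is counted. The Synopsis row on telephone contact, section 7.4 and CRF 7 all provide for lost patients; the Synopsis row and CRF 7 also provide for deceased ones. Section 6.3 requires signed consent and at least 7 years of follow-up. Section 7.4 has unavailable fields crossed out, and section 8.3 asks for all seven CRFs, completed, in each patient's folder.

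**The concern.** A crude percentage is a sound measure of risk when every knee has been watched for the same length of time. Here that is not so, for two reasons.

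First, operations span five calendar years and are assessed at one later contact, so time at risk differs by up to about five years before anyone is lost. If the two inserts were used in different parts of the 2011 to 2015 window, the insert with the longer follow-up accumulates more events at the same underlying rate.

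Second, for a lost or deceased patient the telephone and visit sources are not available and only the medical records remain. A missing CRF 6 does not by itself separate no event from no observation. If such knees stay in the denominator, later events are unseen and the percentage is too low. If the share of patients reached differs between inserts, a difference can appear, or a real one can be hidden, without any difference in risk.

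At stake is the comparison of non-revision safety outcomes between the inserts. The survival endpoints are not touched by this point.

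**Working it through.** **The plan's own figure.** The documents state no figure for reinterventions or complications. The one calculated figure, 152 implants per group, reproduces exactly from section 10.1 (97.2% and 97.7% survival, 4-point margin, 80% power) with one-sided alpha 5%. It concerns the primary endpoint and is used below only to turn percentages into knees.

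**Inputs.** Operation dates are from section 6. The documents give no loss rate, death rate, event risk, event timing or contact date, so all of these are assumed.

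**A. No loss, unequal follow-up.** Assume contact in April 2023, the date of ethics approval of version 02. Follow-up then runs from about 7.3 years (December 2015) to 12.3 years (January 2011). Assume the same constant hazard in both groups with 7-year risk R, so the risk by t years is 1 − (1 − R)^(t/7).

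| R | t = 7.3 | t = 9.3 | t = 11.3 | t = 12.3 |
|---|---|---|---|---|
| 5% | 5.2% | 6.6% | 8.0% | 8.6% |
| 10% | 10.4% | 13.1% | 15.6% | 16.9% |

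A two-year gap in follow-up (9.3 against 11.3 years) makes equal hazards look like 13.1% against 15.6%. The outer columns are a bound that would need one insert used only at the start of the window and the other only at its end. The documents do not say how insert use was spread over the period. If events cluster early, the gap shrinks.

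**B. Loss, with lost knees kept in the denominator.** A share L of knees is lost uniformly over 7 years and later events are unseen. With constant hazard and H = −ln(1 − R), the mean chance that a lost knee has its event before loss is 1 − R/H:

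- R = 5%: H = 0.05129, mean 0.0252
- R = 10%: H = 0.10536, mean 0.0509

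Crude percentage = (1 − L)·R + L·(1 − R/H).

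| L | R = 5% | R = 10% | relative understatement |
|---|---|---|---|
| 10% | 4.75% | 9.51% | about 5% |
| 20% | 4.50% | 9.02% | about 10% |
| 30% | 4.26% | 8.53% | about 15% |

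Now suppose 80% of events fall evenly in year 1 and 20% evenly in years 1 to 7. The share seen in lost knees is 0.8·(1 − 0.5/7) + 0.2·(1 − 4/7) = 0.829. The ratio of crude to true risk is 1 − L + 0.829·L, which is 0.983, 0.966 and 0.949: an understatement of about 2% to 5%.

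**C. Records cover only the first year for unreached knees.** With events spread evenly over 9.8 years (mid-2013 to April 2023), the ratio is 1 − L + L/9.8, which is 0.910, 0.820 and 0.731: an understatement of 9%, 18% and 27%. If instead 80% of events fall in year 1, the ratio is 1 − 0.2·L and the understatement is 2% to 6%. Large values therefore need both short records and late events.

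**D. Unequal loss, equal true risk, 152 knees per group.** With L = 10% in one group and 30% in the other, case B gives 7.2 against 6.5 events (R = 5%) or 14.4 against 13.0 (R = 10%). Case C with a true risk of 10% gives 9.1% against 7.3%, about 13.8 against 11.1 knees.

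**E. CRF 6: sections set side by side.** Section 8.1 item 6 triggers the form only when there is a complication. The introduction to section 8.1 requires CRF information for each included patient, section 7.4 requires forms on loss to follow-up, and section 8.3 requires all seven. Crossing out unavailable fields works only on a form that has been opened. The text does not settle whether a knee with no known event has a CRF 6, or how no event is told apart from unknown.

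**The case against.** The strongest counter-argument is that the documents never say lost or deceased knees count as event-free. A reader might infer this from the event-triggered wording of CRF 6, but it remains an inference. Section 10.2 leaves the denominator open, and contacted or visited patients would be an equally possible choice. Read literally, the consent and 7-year criteria in section 6.3 would remove most lost and deceased patients, which would make the problem one of selection rather than dilution. CRF 7 identifies who was reached. It also records reoperations, so reinterventions do not rest on the event-triggered form alone. Events before loss may be in the medical records. The CRFs are an annex that is not reproduced, so they may already hold event dates or a box for no event.

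All of that stands. It rules out saying that the plan's percentages are biased low by a known amount, and it rules out saying that the forms lack dates. It does not justify the analysis as written. The Synopsis, section 7.4 and CRF 7 treat lost or deceased patients as part of the population to be described, so the documents pull both ways and section 10.2 does not decide. Contact status without a date of last observation also does not give time at risk. And the unequal follow-up in part A remains even if every patient is reached.

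It is also fair that dates of minor non-surgical complications may be unreliable, so time-to-event analysis does not suit every item in this endpoint.

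**Conclusion.** The concern holds in a limited form. Section 10.2 compares reinterventions and postoperative complications as crude percentages, without a denominator or observation time, in a cohort whose follow-up differs by up to about five years and in which loss and death are expected. This goes beyond missing detail, because the stated comparison can mislead if the inserts differ in follow-up length or in the share of patients reached.

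The size cannot be determined from the documents. If lost knees are kept in the denominator and 10% to 30% are lost uniformly, the relative understatement is roughly 2% to 15%, depending on how early events occur. It is larger, up to 27% in the scenarios tried, only if records cover just the first year and events are spread evenly. With unequal loss, the false difference in these scenarios is about one to three knees per 152. No loss rate, event risk or contact date in these figures is a study value.

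The point affects secondary safety endpoints only. It is a worthwhile and cheap improvement.

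**What to change.** **Forms.** Reconcile section 8.1 item 6 with sections 7.4 and 8.3, so that it is clear CRF 6 is completed for every knee. Record *none / present / not ascertainable* and the date to which the knee was observed. Check that the annexed CRFs capture the date of each complication and of any reoperation without removal; add those fields if they do not.

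**Section 10.2.**

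- Analyse reinterventions and datable postoperative complications as time to first event. Use cumulative incidence with death as a competing event, or Kaplan-Meier censored at last ascertainment. Compare the groups by log-rank or as rates per observed knee-year.
- Keep number and percentage with Chi-square or Fisher for intraoperative complications, which do not depend on later follow-up.
- For minor complications that cannot be dated, report percentages among knees with ascertained status, state that denominator, and give the number not ascertainable by group.
- State how knees of lost and deceased patients enter each analysis, consistently with section 6.3.

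**Cost.** A few fields on paper forms and an extra analysis. Kaplan-Meier and log-rank are already planned; if cumulative incidence with competing death is chosen, confirm that the named software provides it. Some dates will rest on recall, and reported risks may be slightly higher than crude percentages.
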